Over the past twenty years, the standard technique for motor systems inquiry has been the use of TMS, which directly investigates neural response while offering excellent temporal resolution. Interestingly aging-related studies of interhemispheric communication have employed this modality and yielded analogous findings to investigations involving fMRI. For example, using a paired-pulse TMS paradigm, Peinemann et al., (2001) reported decreases in levels of interhemispheric inhibition (IHI) across increasing age, a finding later replicated by Talelli et al. (2008a; 2008b). Using a separate, but related measure called the ipsilateral silent period (iSP), Sale and Semmler (2005) reported that their elderly samples reported a significantly shorter duration of ipsilateral inhibition; a finding recently replicated by Fujiyama et al., (2009) and our own lab (McGregor et al., 2011; 2013). Recent work has shown that in older adults declines in unimanual motor performance are associated with decreased duration of the ipsilateral silent period (McGregor et al., 2011; Fling et al, 2011) and changes in excitability of the ipsilateral hemisphere (Bernard & Seidler, 2011; Langan & Seidler, 2010). The implication of these findings is that aging is associated with decreased interhemispheric inhibition, which may be driving declines in motor performance. For example, Bernard & Seidler used transcranial magnetic stimulation to measure motor evoked potentials in the ipsilateral cortex of younger and older adults. The group found that older adults had larger motor evoked potentials in the ipsilateral cortex indicating a decrease in interhemispheric inhibition as compared to younger adults. Importantly, the group also found a somewhat proportional increase in reaction time in the older group respective of the group differences in evoked response amplitude. In our own lab, we have recently shown that duration of ipsilateral silent period, also associated with interhemispheric inhibition, is negatively correlated with age and motor performance in sedentary older adults (McGregor et al., 2011; 2013). We plan to employ transcranial magnetic stimulation both inside and outside of the MRI environment to assess the effects of aging related alteration of GABA receptor function on measures of TMS (iSP, IHI) that are believed to reflect GABAergic activity. Using a battery of assessment TMS measures (i.e. – no cortical modulation – NOT repetitive TMS), we will assess changes in a GABAergic receptor function due to motor learning and exercise.

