Single pulse measures: Four single-pulse TMS measures will be taken: size and latency of Motor Evoked Potential (MEP) in right FDI muscle at resting motor threshold, duration of ipsilateral silent period (iSP), and MEP recruitment curves (RC). Electromyography (EMG) will be taken from the FDI muscle on both hands. Muscle activation will be monitored with a real-time oscilloscope software package (BrainSight 2.3; Rogue Research). A MagVenture x100 magnetic stimulator (MagVenture, Denmark) and a focal figure of 8 coil will be used to stimulate the left primary motor cortex during the initial mapping procedure. The coil will be placed tangential to the scalp with the handle pointing backwards and 45° away from the midline for stimulation. The scalp site corresponding to the lowest stimulator output sufficient to generate a magnetic evoked

potential of at least 50 mV in 6 out of ten trials will be defined as the area of lowest motor threshold (LMT), also known as the “hotspot”. The MEP size measure will be taken using ten stimulations of the left primary motor area FDI hotspot at LMT. The right FDI motor hotspot will be assessed using the same procedure, but with the left hand and stimulation delivered to the right motor cortex.

The ipsilateral silent period will be determined using a longstanding method (Wasserman et al. 1991). For ipsilateral silent period, the left FDI muscle will be contracted via pinch grip at 25% maximal voluntary contraction (determined by grip dynamometer) and an 80% LMT stimulus will be delivered to the left primary motor area FDI “hotspot”, previously determined by an initial sensitivity assessment. Stimulator output equivalent to 150% LMT is delivered to the left FDI hotspot. FDI recruitment curves, a measure of cortical excitability, will be generated by stimulation at the LMT hotspot over progressively increasing intensities. Testing proceeds by placing the coil at the hotspot and recording 5 stimuli in 10% increments beginning at an intensity of 10% below LMT threshold. Data collection for the RC will be terminated when a plateau of the sigmoidal curve is observed. The slope of the RC will be generated from the data using linear regression.

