Our overarching specific aims are to link upper extremity motor performance with changes in GABA physiology that are affected by aging. We will be powering on our least sensitive comparison, which is likely change in MRS after aerobic exercise intervention. Given that we expect greater variability in older adults respective of motor performance and cortical plasticity, we set a moderate effect size for group comparisons at baseline ($d=.5$) and will recruit 40 healthy adult participants. For the aerobic intervention, we are afforded a large effect sizes (1.33 to 1.67) based on the demonstrated efficacy of the aerobic intervention (Nocera et al., 2017). Further, data from our recent work has shown a somewhat linear relationship between $VO_{2\max}$ and levels of interhemispheric inhibition (McGregor et al., 2017). Under this model, a sample size of 20 per group will give us an approximate effect size of .83 for the MRS and TMS measures. Equally important, from the standpoint of our sample size, is that the data gathered on the other outcome measures would be invaluable in fully powering future work. Dropout is a concern for any intervention. As such, we will plan to enroll an additional 8 older participants (as needed) to reach the needed sample size of 20 per group.

REDCap

This study will utilize REDCap issued through the Atlanta Veterans Health Care System. Only deidentified data will be entered in REDCap by VA credentialed research personnel to run data analysis.

Protection Against Risk

Protection against risks introduced due to cognitive testing, MRI and TMS involved have been presented above in Section 7 – Possible Discomforts and Risks.

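### Does the recruitment-curve slope need a stated plateau rule and fitting range before it can be compared before and after exercise?

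*Combined protocol and SAP*

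**What the plan says.** Section 6, TMS Measures, single pulse measures, opens with "Four single-pulse TMS measures will be taken": MEP size, MEP latency, ipsilateral silent period and the recruitment curve (RC). For the RC it specifies "recording 5 stimuli in 10% increments beginning at an intensity of 10% below LMT threshold". It ends with a judgement: "Data collection for the RC will be terminated when a plateau of the sigmoidal curve is observed". The summary statistic follows: "The slope of the RC will be generated from the data using linear regression".

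The section gives no numerical plateau rule, highest intensity, number of levels or fitting window. It does not say whether the steps are in units of LMT or of stimulator output. No other section supplies these.

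Two other places give the TMS battery its role. Section 4, Transcranial Magnetic Stimulation, says "we will assess changes in a GABAergic receptor function due to motor learning and exercise". Section 10 says "a sample size of 20 per group will give us an approximate effect size of .83 for the MRS and TMS measures".

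**The concern.** The plan itself calls the curve sigmoidal, yet it summarises the curve by a straight line. The lower end is fixed at one step below LMT. The upper end is wherever the operator sees a plateau, and nothing ties the post-intervention stop to the pre-intervention stop. A line through a curve that rises and then flattens becomes shallower with each flat point added. Two sessions with the same physiology can therefore give different slopes.

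At stake is the pre/post change in this measure. Stopping points that vary at random would add noise to a comparison planned with 20 per group. Stopping points that differ by arm would add bias. The remedy also looks cheap: a plateau rule, a stated range and no new data.

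**Working it through.** The plan states no RC figure, so there is none to reproduce.

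**Inputs.** From section 6: start 10% below LMT (taken as 90% LMT), 10% steps (taken as % of LMT), 5 stimuli per level, sigmoidal shape. Assumed, because the documents give no values: a Boltzmann curve with midpoint S50 of 115 to 130% LMT and steepness parameter k of 5 to 10; first stop at the first level reaching 95% of plateau; all levels entering the regression.

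**Formulas.** Height as a fraction of plateau: y(I) = 1/(1 + exp((S50 − I)/k)). Least-squares slope: b = Σ(I − Ī)y / Σ(I − Ī)².

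**Worked case, S50 = 120, k = 7.**

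- Levels 90 to 150: y = 0.0136, 0.0543, 0.1933, 0.5000, 0.8067, 0.9457, 0.9864; Ī = 120; b = 53.15/2800 = 0.01898.
- Adding 160 (y = 0.9967): Ī = 125; b = 70.53/4200 = 0.01679.
- Ratio 0.885, a fall of 11.5% on an unchanged curve.

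**Change in slope from the first extra level.**

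| S50 | k = 5 | k = 7 | k = 10 |
|---|---|---|---|
| 115 | −10.0% | −12.6% | −12.0% |
| 120 | −9.8% | −11.5% | −9.4% |
| 125 | −3.0% | −8.0% | −8.9% |
| 130 | −4.5% | −7.8% | −6.2% |

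The median is −9.2% and the mean −8.7%. A wider grid (S50 110 to 140, k 4 to 15) gives −17.6% to +2.7%, median −7.9%. If collection stops at 90% of plateau, the first extra level can raise the slope by up to 13.8%, because the curve is still rising. If the steps are in stimulator output and LMT is 40 to 60% of output, one extra level costs 15% to 18%.

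**Noise.** Simulated SD of the within-person log change on an unchanged curve, with extra plateau levels drawn independently at each visit (log-normal trial noise):

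| Trial CV | Extra levels | All levels | Range common to both visits | Reduction |
|---|---|---|---|---|
| 0.2 | 0–1 | 0.112 | 0.087 | 22% |
| 0.4 | 0–1 | 0.183 | 0.172 | 6% |
| 0.6 | 0–1 | 0.262 | 0.254 | 3% |
| 0.8 | 0–1 | 0.340 | 0.341 | none |
| 0.2 | 0–2 | 0.152 | 0.084 | 45% |
| 0.4 | 0–2 | 0.207 | 0.170 | 18% |
| 0.8 | 0–2 | 0.335 | 0.323 | 4% |

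**Bias.** If the post visit always stops one level later, the mean log change is −0.098, or exp(−0.098) − 1 = −9.3%; on the common range it is 0. A shift shared by both arms cancels in the difference between arms. Only a shift that differs by arm biases that comparison.

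**Cost of the replacement.** Let k go from 7 to 5 at S50 = 120, a true steepening of 7/5 − 1 = 40%.

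- Each visit stopped at its own plateau: 0.01898 to 0.02248, +18%.
- Common range 90 to 140: 0.02064 to 0.02248, +9%.

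Simulated mean/SD of the change, with 0–1 extra levels:

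| True change | Trial CV | All levels | Common range | Difference |
|---|---|---|---|---|
| 40% steepening | 0.2 | 1.13 | 0.95 | −16% |
| 40% steepening | 0.4 | 0.74 | 0.49 | −34% |
| 40% amplitude rise | 0.2 | 3.06 | 4.00 | +31% |
| 40% amplitude rise | 0.4 | 1.83 | 1.95 | +7% |

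A repeat simulation gave the same pattern: for steepening, 1.22 to 0.99 and 0.78 to 0.51; for amplitude at CV 0.4, 1.86 to 2.01.

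**The case for a change.** The strongest case for a change is that the gap is real and cheap to close. The plan describes a sigmoid, fits a line and leaves the last point to the operator. Cortical excitability is the subject of the study's title. The documents mention no masking of assessors, so a judgement made at the stimulator could drift with arm. A few sentences would remove a choice that could otherwise be made after the data are seen. With low trial noise and stopping that varies by up to two levels, a common range nearly halves the SD.

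The gap and its direction stand. Three things weaken the rest.

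- That every level enters is the plain reading of the sentence, but it is not stated. Fitting only the rising part is also compatible with it.
- The large gains need low trial noise or two-level variation in stopping, and the documents give neither. Absence of a masking statement is not evidence that stopping differs by arm.
- The remedy is not free. The common range gains for amplitude and loses for steepness, and the documents do not say which of these exercise would change. A sigmoid fit avoids the dependence on stopping point in noise-free data, but 5 stimuli per level limit its precision. Neither it nor a simple rising-segment line was uniformly better.

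The link to the trial's conclusions is also thin. Section 4 names the silent period and interhemispheric inhibition as its GABA-related measures. Aim 3 concerns intracortical and interhemispheric inhibition. TMS during motor learning uses paired-pulse protocols. The effect size in section 10 follows a sentence on interhemispheric inhibition and does not rest on the RC.

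**Conclusion.** No change to the plan follows. If all levels enter the line, the slope does depend on where collection ends: about 3% to 13% lower for the first extra plateau level, under assumed Boltzmann curves with a 95% stop and steps in LMT units. The size, and with early stopping even the sign, depends on parameters that the documents do not give.

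For the trial, this means some added noise in one single-pulse measure that no specific aim names and that does not set the sample size. The added noise is small or absent at the higher trial noise levels examined when stopping varies by one level. Bias between arms would need stopping to differ by arm, which nothing in the documents indicates. The obvious alternative exchanges protection against stopping differences for sensitivity to steepness, so it is not a clear improvement. The plateau criterion, the levels fitted and the step unit are details that analysts can fix and report when the curves are processed.
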